10.13.2. General Considerations For Data Analyses and Handling

10.13.2.1. Software

Programming will be performed in a HARP™ environment using SAS Version 9 or a later release and S-Plus Version 7 or later release. The population PK analysis will be completed using NONMEM software, Version 7 (ICON Development Solutions). Data set handling, graphical analysis and post-processing of table files will be performed with R Version 3 or later. The platform(s), operating system(s), Fortran compiler and any other software used will be described in the study report.

10.13.2.2. Data Set Preparation

POP PK analysis with NONMEM needs the data to be arranged in a specific format along with a number of indicator variables integral to the software. A summary of the dataset specifications, indicator variables and their description are given in Section 10.13.6. Variables included in the final data set will depend upon the best fit population model(s) and influential covariate(s) in this population. Therefore all indicator variables may not be included in the final model. If data sets are modified or reformatted over the course of the analysis, the file name of each version of the data set will be unique. For each generated data file, the source file and the SAS or R/S-Plus script file used for data manipulation will be archived.

The POP PK dataset will be generated on multiple occasions as the study progresses to support the planned interim analyses - up to two main interim analyses are currently planned. Any dataset generated will include all available evaluable TQ PK data up to that time. The dataset aggregation and initial modelling setup work may begin earlier than the planned interim analyses to aid any pre-programming, preliminary structural model establishment and generation of simulation and graphing scripts.

Any deviations from the analysis plan will be described in detail in the study report.

10.13.2.3. TQ Population PK dataset

For the TQ population PK analysis, patient demographic data (e.g. gender, age, weight, body mass index (BMI)), treatment, dosing and sampling dates and time will be extracted from the study database and merged with TQ plasma concentration data extracted from SMS2000 for the TQ PK population. The POP PK analysis compliant data file will be produced by or under the direct auspices of the programming support within the Clinical Statistics or Clinical Pharmacology, Modelling and Simulation groups, GlaxoSmithKline.

Due to the small study size and sparse nature of the PK sampling schedule, data from the previous adult studies with more extensive sampling (e.g. the Phase 2B dose ranging study TAF112582) may be included to stabilise the structural model as deemed appropriate. SAS or R may be used to merge the pediatric TQ PK data with adult TQ PK data. All such POP PK dataset processing scripts will be archived.

10.13.2.4. Archival Of Data Sets

Data sets, R-script used for data manipulation and/or graphics, NONMEM control stream files, NONMEM output files, NONMEM output processing programs and files obtained from processing of NONMEM output will be archived.

10.13.3. Handling of Missing Data

10.13.3.1. PK Data

If dosing and/or sampling times are missing, the relevant concentrations will be deleted from the analysis dataset and summarized in a deletion record listing by the programmer. Samples listed as having no sample (NS), no result (NR) or insufficient sample (IS) will be excluded from the PK data set and also included in the deletion record listing.

10.13.3.2. Subject Demographics

Imputations of any continuous covariate value will only be performed if the variable is missing for less than 10% of the subjects and the variable is deemed necessary for the modelling effort. For continuous covariates, missing values for an individual subject will be imputed as the gender-specific median value for the study. Any changes to the imputation methods will be justified and documented. If the percentage of missing data is greater than 10%, the variable will only be evaluated in exploratory graphical displays. There may not be imputation for any missing categorical covariate value.

10.13.3.3. Handling of Data Below the Lower Limit of Quantification

TQ concentrations below the respective lower limit of quantification (LLQ) for the bio-analytical assay will be reported as NQ (Below Quantification Limit, BQL). All NQ values will be set to "." in the population PK dataset. Individuals with all plasma concentrations reported as NQ will be included in the data set. However, a likelihood estimation method (M3) for these BQL data will not be implemented (Ahn et al) and the BQL observation rows will be ignored during model building.

10.13.3.4. Handling of Outliers

Concentration results inconsistent with the expected PK behaviour of TQ may be excluded from the modelling after investigation about possible sampling/labelling errors. Outlier detection will be based initially on visual examination of individual and pooled PK profiles. However, the final model may be retested with and without inclusion of these data points. The exclusions will be listed in the report.

10.13.4. Population PK Modelling

The POP PK analysis will be based on non-linear mixed-effects models. The analysis will be performed as recommended by the *FDA, Population Pharmacokinetics Guidance for Industry* document [FDA, 1999]. Mixed-effects models describe the influence of both fixed effects and random effects on a dependent variable, e.g. concentration or clinical endpoint. Fixed effects, THETA (θ) in NONMEM notation, are factors that are either measured or controlled. Random effects include residual error (ERR), epsilon (ϵ) in NONMEM notation, and between subject random effects, ETA (η) in NONMEM notation.

Population mixed effects models include the basic components:

- The structural model, which predicts the plasma concentration as a function of time and dose.
- The covariate model component, which describes the influence of fixed effects (e.g. demography, disease, treatment, concomitant medication) on the PK model population parameters.
- The between-subject variance component, which describes the inter-individual variation in PK parameters (after “correction” for fixed effects). Inter-individual or between-subject variability will be initially modelled using an exponential error model.
- The residual error model components describe the underlying distribution of the error in the measured PK variable. Various error models are available to choose from based on emerging data. The goodness-of-fit plots and any potential biases therein will aid selection of an appropriate residual variability model e.g., additive, proportional, additive plus proportional or exponential.

A visual predictive check (VPC) method will be utilized to evaluate the adequacy of the final model, including the effects of statistically significant covariates. Statistics of interest including mean derived PK parameter values will be calculated from this model based analysis.

10.13.4.1. TQ Population PK Analysis

10.13.4.1.1. Base Model

A structural model for the available TQ PK data from pediatric population will be built first, including error models. Initial selection of the simplest structural POP PK model, to be used as a valid base model, will be based on but not limited to the minimum objective function value, plausibility of parameter estimates, goodness-of-fit plots and VPC plots. The most appropriate between-subjects

variability and residual error model, will be identified and the resulting model called a BASE model. If needed different estimation methods available in recent NONMEM versions may be tested to characterize the sparse PK data.

Due to the sparse PK sampling and few subjects, only key parameters of interest may be estimated (e.g. clearance – TQ CL) as data permit. Other PK parameters (e.g. absorption rate – TQ KA) may be fixed to the population estimates obtained from the TQ POP PK analysis of data from the dose ranging Phase 2B study in adult population (TAF112582). The random effect on these parameters may be estimated as data permit. If needed, the TQ PK data from those studies may also be included in the analyses dataset to provide stability to the POP PK structural model.

Any deviations from such planned analysis will be described in detail in the study report.

10.13.4.1.2. Covariate Inclusion

Once a BASE model has been identified, covariates will be added as necessary, using predefined strategy. Currently, the doses selected for the TEACH study are based on allometric scaling of clearance based on weight. Thus while not mandatory, patient weight is likely to be included as a significant component of the structural model and will be primarily guided by emerging pediatric PK data. While unlikely that other covariates will be included in the model due to small study size, the effects of subject demographic characteristics (e.g. age, body mass index (BMI)) may be examined as data permit. The final model shall have no redundant factor but the strategy shall ensure that no significant factor is missing.

Covariate model building may be undertaken once data from all pediatric patients is available at the end of the study. The covariate modelling approach will consider the step-wise process consisting of a forward and a backward selection procedure as appropriate based on emerging data.

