4. STUDY DESIGN

- TAF113577 is a prospective, open-label, multicenter, non-comparative, single-arm study. All subjects will receive CQ and open-label TQ.
- Potential subjects can be identified, pre-screened, and begin off-study treatment with CQ, after which sites will have up to 48 hours to obtain full consent/assent, as applicable. Upon consent, subjects will be treated with tafenoquine on Day 1, then attend seven follow-up visits (Days 3, 8, 15, 29, 60, 90 and 120). The total follow-up period will be 120 days.
- During the follow-up period, sites have the option of performing non-PK visits (Days 8, 90 and 120) at the subject's home.
- Subjects must have a blood smear that is positive for *P. vivax* at pre-screening. Blood smears will be taken at Day 1 (screening) and at Day 8 to confirm the parasite has cleared. Additional parasitological assessments will be conducted on visit Days 29, 60, 90 and 120.
- At the Day 1 visit subjects will be screened for G6PD deficiency by a quantitative assay and the result will be determined as a percentage of the predetermined median enzyme activity of the site. All subjects must have a minimum G6PD assay value of 70% to be enrolled.
- A total of 60 pediatric subjects will be enrolled. The main cohort will consist of subjects aged ≥ 2 years to < 16 years with no restriction on gender. Subjects will be dosed according to four weight bands.
- Within the total of 60 enrolled pediatric subjects, a second cohort of up to 6 infants aged ≥ 6 months to < 2 years (weighing ≥ 5 kg) may be recruited following completion of a planned first interim analysis (see below).
- An interim analysis will be conducted once sufficient data from 16 subjects is available to assess PK and safety parameters. If needed, a second interim analysis may be conducted after a total of 32 subjects have enrolled. The primary analysis population will be the PK evaluable population.
- A subject is considered to have completed the study if they attend all treatment and follow-up visits. A PK evaluable subject is defined as one with a minimum of one PK sample from Days 3, 15, 29 and 60.
- The final safety analysis will take place when all 60 enrolled subjects have completed the study.
- A population PK model will be used to estimate the clearance and thus exposure of TQ for each of the weight bands in the main cohort [$AUC(0-\infty) = \text{Dose/Clearance (CL)}$].

[figure not shown]

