4.4.1. Dose Justification in Cohort Aged <2 years

There is no lower age limit below which infants and children are not susceptible to vivax malaria. There is, however, a balance to be struck in terms of collecting data sufficient to define an appropriate dose for infants, versus limiting the number of study related assessments to which this highly vulnerable group are subjected. Where possible, PK data from an additional cohort of six infants aged ≥ 6 months to <2 years (weighing ≥ 5 kg) will be obtained to define dosing in infants down to 6 months. Available data from this cohort will be combined with data obtained from the main cohort as part of the final population PK analysis. The lower age of 6 months is based on the age at which G6PD enzyme activity reaches maturity. The pediatric population PK model used for dose prediction has been developed based on adult patient data and includes an allometric function for weight-based dosing. Allometric scaling accounts for size differences only and not age-related changes in metabolizing enzymes or renal function. However, the generalized functional immaturity in metabolizing enzyme activity and renal function approach adult levels about 6 months after birth [Kearns, 2003]. Thus, the model is appropriate for dose prediction in this cohort.

The decision to enrol subjects aged ≥ 6 months - <2 years will be based on a review of exposure data as well as of safety results from the first interim analysis. Particular attention will be paid to the reporting of adverse events related to decreases in hemoglobin (Hb), methemoglobin (metHb) levels, increases in creatinine, and any reports of phototoxicity.

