9.4.2. Secondary Analyses

The overall safety and particularly of key endpoints such as gastrointestinal tolerability, clinically relevant drops in hemoglobin and incidence of AEs will be assessed. The ophthalmic assessments of visual acuity, keratopathy and retinopathy will be summarized.

The recurrence-free efficacy at 4 months will be estimated at the interim and final analyses. The targeted exposure in the pediatric study population is expected to match the high level of recurrence free efficacy observed in adults. Although there is no control group to compare the background recurrence rates, the overall estimate of recurrence rates will help compare the exposure-efficacy response in this study to the observed response in the efficacy studies in adults.

If data has been acquired in infants aged ≥ 6 months to < 2 years, it will be included in the main PK model and will contribute to the overall assessment of TQ exposure by weight band and dose setting in this age band.

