12.8. Appendix 8 – Tafenoquine Pediatric Dose Extrapolation

Document Number: 2014N199461_03

Division: Worldwide Development

Retention Category: GRS019

Information Type: Clinical Pharmacology Modelling Report

Title:

Tafenoquine Paediatric Dose Extrapolation

Compound Number: SB-252263, Tafenoquine

Effective Date: 23/04/2014

Description:

Extrapolation of the adult population-PK modelling to paediatric dosing. Identification of doses and weight bands using random-space sampling with optimality.

Subject: Tafenoquine, paediatric, allometry, dose selection

Author's Name and Functional Area:

PPD [redacted] & PPD [redacted]
Clinical Pharmacology Modelling & Simulation

PPD [redacted]
Clinical Statistics

Approved by:

PPD [redacted]
Clinical Pharmacology Modelling & Simulation

Tafenoquine Paediatric Dose Extrapolation

PPD

23/04/2014

1. Introduction

Tafenoquine has been dosed in a Phase 2b dose-ranging study in adults with extensive pharmacokinetic data for single adult doses of 50, 100, 300 and 600 mg. A population PK analysis (to be reported) using a two-compartment model with first order absorption and random effects on volume and terminal phase half-life (beta) identified bodyweight to be a significant determinant of exposure. The allometric power for clearance was approximately 0.5, in contrast to traditional estimates of 0.75. The inclusion of bodyweight allometry into the model was highly statistically significant.

Assuming a target exposure equivalent to the adult dose of 300 mg, we propose using allometry to optimally select doses and weight bands that provide the best matching of paediatric AUC(0-inf) to that of adults. The justification for the selection of 300 mg will be discussed elsewhere. The proposal is to use the parameters for the adult model, and assume that there are no developmental effects on the apparent clearance of tafenoquine for the age (and weight) ranges to be treated.

2. Methods

The adult population pharmacokinetic model used to describe the Phase 2b dose ranging study was the standard two-compartment model with first order absorption. Bodyweight is part of the model and the full equation takes the form;

$$C(t) = \text{Dose} * ((\text{BWT}/60)^{p\text{BWT}} * (A * \exp(-\text{Alpha} * t) + B * \exp(-\text{Beta} * t) - (A+B) * \exp(-\text{KA} * t))).$$

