3.1. Pharmacokinetic Model

The Phase 2b adult data was described using a two-compartment model with first-order absorption and integral allometry that incorporated weight as a determinant of exposure. The model was parameterised in terms of macroconstants, A, B, Alpha and Beta and the full equation takes the form;

$$(t) = \text{Dose} * ((\text{BWT}/60)^{**} - \text{pBWT}) * (\text{A} * \exp(-\text{Alpha} * t) + \text{B} * \exp(-\text{Beta} * t) - (\text{A} + \text{B}) * \exp(-\text{KA} * t)) + \text{s2}.$$

[figure not shown]
where s2 is the residual. Parameters A and B are random effects and share the same log-normal distribution with inter-subject variance s2b1. The terminal elimination rate, Beta, is also a random effect with variance s2b2 with no correlation to A and B. The final parameter estimates from the adult model are given in the table below. AUC(0-inf) was estimated from the macroconstant parameterisation as $\text{Dose} * ((\text{BWT}/60)^{**} - \text{pBWT}) * (\text{A}/\text{alpha} + \text{B}/\text{Beta} - (\text{A} + \text{B})/\text{KA})$, and clearance calculated from AUC for both population and individual subjects.

Table 7 Pharmacokinetic Parameters for the Model (above)

Parameter	Value	Units	Notes
A	0.8586	ng/ml/mg	Macroconstant with V2/F
B	0.4813	ng/ml/mg	Macroconstant with V2/F
Alpha	0.4380	/day	Distribution half-life
Beta	0.0415	/day	Elimination half-life
KA	3.3073	/day	Absorption Rate
pBWT	0.5217	NA	Scaling power for BWT
s2b1	0.2766	NA	SDLOG(A,B) variability
s2b2	0.1695	NA	SDLOG(Beta) variability
s2	0.2657	NA	SDLOG(Resid) residual

A population of 1000 paediatric subjects is simulated for each of 1000 trials based on a log-normal weight distribution with mean 3.36 and log standard deviation 0.66. This gives a mean bodyweight of 28.9 kg and probabilities of <1%, 5%, 23%, 33% and 36% of being in weight bands 0-5, 5-10, 10-20, 20-35 and >35 kg respectively (see [Figure 10](#) below). From this population subjects are then drawn with or without stratification. Since subjects of less than 5 kg will not be recruited, stratification only impacts the proportions in bands 2-5. Without stratification, bands 2 and 5 will be under-represented, which may have consequences for the estimation of allometric scaling and hence patient exposure at bodyweight extremes.

Figure 10 Cumulative Probability Distributions for Recruitment by Weight Band (above)

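### An infant age effect on clearance is left to optional covariate selection, with no infant/older clearance ratio or interval required, so infant exposure simulations can rest on weight alone by default

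*SAP*

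**What the plan says.** **Size of the infant cohort.** Protocol Section 4 states "A total of 60 pediatric subjects will be enrolled" and, within that total, "a second cohort of up to 6 infants aged" 6 months to under 2 years.

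**What the weight model covers.** Protocol 4.4.1 states "Allometric scaling accounts for size differences only and not age-related changes in metabolizing enzymes or renal function". It then argues that enzyme and renal function are near adult levels by about 6 months, so the model can be used for this cohort. The dose extrapolation in Appendix 8 says it will "assume that there are no developmental effects on the apparent clearance of tafenoquine".

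**How infant data are used.** Protocol 9.4.2 says of any infant data that "it will be included in the main PK model and will contribute to the overall assessment of TQ exposure by weight band", and also to dose setting for that age band. SAP 10.13.4.1.3 uses the final model for the exposure simulations.

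**How age enters the model.** In SAP 10.13.4.1.2 weight is the expected covariate. For the rest: "While unlikely that other covariates will be included in the model due to small study size". Age and BMI may be looked at if the data allow, with forward and backward selection considered where appropriate. The governing rule is "The final model shall have no redundant factor but the strategy shall ensure that no significant factor is missing". The section refers to a predefined strategy, but the SAP gives no entry or removal threshold, no form for the age term and no precision target. SAP 10.13.4 speaks of checking the effects of statistically significant covariates.

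**What is reported on infants.** Infant AUC by weight band is a secondary endpoint, if data permit. SAP 10.13.7 displays results by age group. Neither document asks for an infant/older clearance ratio or its interval.

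**The concern.** The infant cohort is the only group in this study that can show whether a weight model built on adults and older children holds below 2 years. Answering that needs an estimate of the infant difference with its uncertainty. The SAP treats the question as covariate selection, and a step-wise search with at most 6 infants will often drop a real difference of moderate size. Infant age and low weight also go together, so a freely estimated weight exponent absorbs part of any age effect.

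If the term is dropped or never tried, the infant simulations carry neither the age effect nor its uncertainty. The secondary infant PK objective and the infant part of the dosing recommendation would then depend on the assumption that the cohort could have checked.

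**Working it through.** **1. Reproduce the plan's exposure figures.** With the Table 7 parameters (protocol Appendix 9, section 3.1), dose-normalised AUC at 60 kg is

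24/1000 × (A/Alpha + B/Beta − (A+B)/KA) = 0.024 × (0.8586/0.4380 + 0.4813/0.0415 − 1.3399/3.3073) = 0.3157.

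Appendix 8 states 0.316. For 300 mg this gives 94.7 (the documents state 95 and 96).

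**2. Between-subject SD of log AUC (equal to that of log clearance).**
- From the adult prediction interval 55–162: ln(162/55)/(2 × 1.96) = 0.276. This agrees with the Table 7 value 0.2766, labelled "SDLOG(A,B) variability".
- Adding the Table 7 variability on Beta (0.1695) gives a simulated log-SD of 0.314. That implies an interval of 51–176, wider than the one stated.
- Range used: 0.276 to 0.314.

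**3. Assumptions the documents do not supply.**
- 6 infants of 6.5–11.5 kg and 54 older children of at least 10 kg, with older children's weights from the Appendix 9 log-normal distribution (log-mean 3.36, log-SD 0.66).
- Individual log-AUC estimation error of 0 to 0.20.
- Weight exponent estimated, children's data only.
- Infant clearance 30% lower at equal weight (illustrative).
- Thresholds p<0.05 and p<0.01.

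**4. Precision of the infant effect.**

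SE = SD × √(1/6 + 1/54) × √VIF, with √(1/6 + 1/54) = 0.430.

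VIF is the variance inflation from estimating the weight exponent. It simulates at 1.4–1.6 across plausible infant weight ranges; 1.55 is used here (√1.55 = 1.245).

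- Favourable end (0.276, no error): 0.276 × 0.430 × 1.245 = 0.148. 95% CI factor: exp(1.96 × 0.148) = 1.34.
- Unfavourable end (√(0.314² + 0.20²) = 0.372): 0.372 × 0.430 × 1.245 = 0.199. 95% CI factor: exp(1.96 × 0.199) = 1.48.

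Even an estimated ratio of exactly 1.0 would leave a lower limit of 1/1.34 = 0.75 or 1/1.48 = 0.68.

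**5. Chance of missing a 30% lower clearance.** Miss = Φ(z_crit − |ln 0.7|/SE), with |ln 0.7| = 0.357.

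| Setting | 0.357/SE | Miss at p<0.05 | Miss at p<0.01 |
|---|---|---|---|
| Favourable | 2.41 | Φ(1.96 − 2.41) = 33% | Φ(2.576 − 2.41) = 57% |
| Unfavourable | 1.79 | Φ(1.96 − 1.79) = 57% | Φ(2.576 − 1.79) = 78% |

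Simulated likelihood-ratio tests of log AUC on log weight, with and without an infant indicator, give about 32–57% and 57–79%. For a 20% lower clearance they give about 66–78% and 84–92%.

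**6. Consequence when it is missed.** In the same simulations the weight-only fit predicts infant AUC at about 0.81 of truth, because the exponent absorbs part of the effect. A schedule built on that fit and aimed at 96 would deliver 96/0.81, about 118.

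**7. What the age-group display could show.** Infants with 30% lower clearance, at a dose otherwise giving 96, would have a geometric mean AUC of 96/0.7 = 137. With 6 infants the 95% t-interval is about 103–183 (SD 0.276) to 99–191 (SD 0.314).

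**The case against.** The SAP is more flexible than a pure significance rule. SAP 10.13.4.1.3 describes the final model as one that has evaluated key clinically relevant covariates and fits the data. SAP 8.5.4 and 10.13.1 say the influence of demographics will be investigated. Infant AUC is its own endpoint, individual AUCs come from post-hoc clearance, results are split by age group, and infants may keep the fuller sampling scheme (SAP 10.13.4.2). A shift towards 137 would probably be noticed. All of this stands. A reader might infer that age can enter only if significant, or that a non-significant result is to be taken as proof that weight alone sets infant exposure. The documents say neither.

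It does not close the gap. A descriptive display puts neither the shift nor its uncertainty into the simulations, and post-hoc estimates from sparse samples tend to be pulled towards the weight-only prediction.

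Adult data may also be pooled to stabilise the model (SAP 10.13.2.3 and 10.13.4.1.1). Adding 158 simulated adults, the number starting in the four tafenoquine groups of protocol Figure 3 (40 + 39 + 43 + 36), lowered the miss rates to about 25% and 47% at the favourable end and 48% and 72% at the unfavourable end. This helps somewhat, but pooling is optional.

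The consequence is also moderate on the plan's own scales. The ratio 118/96 = 1.23 lies inside 55–162 and inside the 77–120 bounds of Appendix 9, and below the 1.5-fold deviation that SAP 10.13.4.2 treats as slight. Protocol 4.4.1 expects near-maturity by 6 months, so 30% is an illustration and not a forecast.

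**Conclusion.** The concern holds as a gap in estimation and reporting. The SAP leaves the infant age effect to optional selection, expects it to be left out, and requires no infant/older clearance estimate, while the resulting model informs dosing in that age band. Under the assumptions listed, a 30% lower infant clearance would be missed in about 32–57% of trials at p<0.05 and 57–79% at p<0.01, and infant AUC would then be predicted at about 0.81 of truth.

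Two stronger readings are not supported. Quoting one miss rate of 55–78% would join two thresholds that the SAP does not state, at the least favourable variability and estimation error. Claiming that pooled infants would distort predictions for older children in the 5–10 kg band conflicts with the assumption used here that older children weigh at least 10 kg.

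The change should be made. Confidence in the direction is good. Confidence in the exact rates is moderate, because infant weights, estimation error, threshold and effect size are all assumed.

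**What to change.** Add to SAP 10.13.4.1.2:

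- If any infant is PK evaluable, the final model will also be refitted with a pre-specified infant effect on clearance (an indicator or a stated age function), with weight in the model.
- The infant/older clearance ratio at equal weight will be reported with its 95% CI, whether or not it is significant.
- Infant exposure simulations will be shown with and without the term.
- A non-significant age term will not be reported as absence of an age effect; the report will state what size of difference the interval leaves open.

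The cost is one extra model run and a few lines of text, with no new data. The drawback is that the infant result will appear with a wide interval, about ×/÷1.3–1.5 with 6 infants and wider with fewer.
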